#### 4. PATIENT SELECTION CRITERIA

Female unilateral BC patients treated at one of the five participating centres with postoperative modern planning-CT based RT alone after breast conserving surgery, and who are aged 40-75 years at the time of RT.

##### **Inclusion criteria:**

- Female unilateral breast cancer patients
- Treated with primary breast conserving surgery for stage I-III invasive adenocarcinoma of the breast or ductal carcinoma in situ (DCIS)
- Age between 40-75 years at time of start radiotherapy
- WHO performance status 0-1
- Planned for radiotherapy alone to the breast with or without the lymph node areas
- Radiotherapy based on planning-CT scan using either 3D-CRT, IMRT, or VMAT/RapidArc
- Written Informed consent

##### **Non inclusion criteria:**

- Male breast cancer patients
- Neoadjuvant or adjuvant chemotherapy
- M1 disease (metastatic breast cancer)
- Medical history of coronary artery disease and/or myocardial infarction and/or atrial fibrillation
- Previous thoracic or mediastinal radiation
- Contraindications to injection of iodinated contrast such as allergy or renal failure
- Pregnancy or lactation

## **Exclusion criteria**

- Atrial fibrillation detected during electrocardiogram before radiotherapy
- Abnormal echocardiography before radiotherapy defined as: LVEF<50%; longitudinal strain  $\leq$  -16%; longitudinal strain rate  $<$ -1%, and/or abnormal wall motion
- Presence of myocardial infarction detected during MRI before radiotherapy
- CTCA or cardiac MRI results before radiotherapy requiring revascularisation

▶ See CRF ELIGIBILITY in appendix for further details

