#### *Anatomical and functional cardiac imaging*

Using a recent advanced echocardiographic technique, automated 2D-speckle-tracking echocardiography / cardiac strain, for detecting and quantifying subtle disturbances in left ventricular systolic function; strain and strain rate were significantly decreased (mean 5%) during the first year following breast RT. In patients with left-sided BC global longitudinal strain and apical strain was diminished. The basal regions showed a compensatory increase in function, though not enough to compensate for the global functional loss resulting in a decrease in the global

longitudinal strain. Tuohinen et al. also showed deterioration in basal anterior strain segments after right-sided radiotherapy, whereas the global function remained unaffected. They also observed with tissue Doppler imaging that RT increased ECHO-ST density in the RV free wall and in the septum at the end of RT in patients with left-sided BC, but there were no changes observed in cardiac ECHO-ST density in patients with right-sided BC.

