### 9.2. Sample Size

The sample size was based on a statistical power of 80%, an alpha-risk of 5%, the definition of the primary endpoint (a decrease in the global and segmental longitudinal strain or strain rate of at least 2.5%) and baseline measurements hypothesis (mean global longitudinal strain before RT : -16.5%  $\pm$  2.1% from Dalen et al, European Journal of Echocardiography : the Journal of the Working Group on Echocardiography of the European Society of Cardiology. 2010) Considering paired test for comparisons, but also possible lost to follow-up due to death or other reason, the inclusion of 250 women is necessary for EARLY-HEART study.

Centre	Recruitment rate per month	Total number of patients to recruit in 1 year
IRSN	4.2	50
UMCG	5	70
TUM-MED	4.6	55
CCUL	2.1	25
ICO	4.2	50
Total		250

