## Appendix

### LOCAL CRF ECHO-ST

**Inclusion Number:** .....

**Date of the visit** : .....

**Date of Birth:** .....

Name and version of the of the ultrasound system:

- General Electric Health Care , version:
- Philips, version:
- Siemens, version:
- Toshiba, veesion
- Other to precise:

Precise if it is : before radiotherapy

6 months after the end radiotherapy

2 years after the end of radiotherapy

- Global longitudinal strain: .....
- Segmental longitudinal strain (Segment 1 to 16) : .....
- Global longitudinal strain rate: .....
- Segmental longitudinal strain rate (Segment 1 to 16) : .....
- Global radial strain : .....
- Segmental radial strain (Segment 1 to 16) : .....
- Global radial strain rate: .....
- Segmental radial strain rate (Segment 1 to 16) : .....
- Left ventricular ejection fraction using Simpson's biplane method: .....
- Left ventricular end-diastolic volume using Simpson's biplane method: .....
- Left ventricular end-systolic volume using Simpson's biplane method: .....
- Left-ventricular end-diastolic diameter using M-mode: .....
- Left ventricular mass measured according ASE/EAE guidelines: .....
- E/A wave ratio : .....
- E/Ea wave ratio (lateral annulus) : .....
- TAPSE (tricuspid annular plane systolic excursion) : .....
- Tricuspid annular S wave : .....
- Pulmonary artery systolic pressure (based on the peak tricuspid regurgitation velocity estimate and by assuming a right atrial pressure of 5 mmHg) : .....
- Left ventricular outflow tract diameter: .....
- Left ventricular outflow tract velocity time integral: .....
- Heart rate: .....
- Cardiac output measured by multiplying heart rate by stroke volume: .....

**In case of abnormal echocardiography before radiotherapy defined as: LVEF<50%; longitudinal strain  $\leq$  -16%; longitudinal strain rate <-1%, and/or abnormal wall motion, the patient should be excluded of the study (exclusion criteria )**

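### The baseline strain exclusion is printed with its inequality reversed: it removes women with normal or strong strain, including the plan's own average woman, and admits women with weak strain

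*Combined protocol and SAP*

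**What the plan says.** - **Section 4, Exclusion criteria.** The definition opens with "Abnormal echocardiography before radiotherapy defined as: LVEF<50"% and continues with "longitudinal strain $\leq$ -16%; longitudinal strain rate $<$ -1%, and/or abnormal wall motion".
- **Appendix, Local CRF ECHO-ST.** The form closes with the same thresholds as an instruction to the site: "longitudinal strain rate <-1%, and/or abnormal wall motion, the patient should be excluded of the study".
- **Section 9.2, Sample Size.** Strain is on a signed, negative scale: "mean global longitudinal strain before RT : -16.5% $\pm$ 2.1"%.
- **Section 2.1, on cardiac imaging.** Loss of strain is loss of function. The basal compensation after left-sided radiotherapy is described as "not enough to compensate for the global functional loss resulting in a decrease in the global" longitudinal strain.
- **Section 3.2.1.** The primary endpoint is a decrease of at least 2.5% in global longitudinal strain or strain rate, so strain is both a selection variable and the primary outcome.

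No section says that the thresholds are to be read as absolute values.

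**The concern.** On the scale of section 9.2 a weaker heart has a less negative strain. A rule meant to remove abnormal hearts should catch values above (less negative than) a cut-off. The printed rule catches values at or below it, and the strain-rate item has the same direction. The LVEF item beside them removes poor function, so one list points two ways. Strain rate is also given in %, without a time unit.

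Three things are at stake.

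- **Population.** Applied literally, the rule builds a cohort of women whose strain is already weak, the opposite of what the word abnormal intends.
- **Consistency between centres.** Section 12.4 has monitors check eligibility in full and record deviations. As printed, a woman at -18% is a deviation and a woman at -12% is not. Five centres recruit. Section 12.3 names a core reading centre for CT angiography and MRI but none for echocardiography. Nothing written ensures that all centres resolve the sign in the same way.
- **Primary endpoint.** Selecting on a variable and then measuring its change produces regression to the mean, and the direction of the inequality decides which way that drift goes.

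**Working it through.** **Inputs.** Mean -16.5% and SD 2.1% (section 9.2); cut-off -16% (section 4 and ECHO-ST form). Assumptions: baseline strain is normal, the cited mean and SD describe the women assessed, and the criterion means global strain (the text says only longitudinal strain, while the form records a global value and 16 segments). The documents give no distribution for strain rate, so that item is not quantified.

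**The plan's own figure.** The documents state no exclusion rate to reproduce. The only stated figure that uses baseline strain is the sample size of 250. It cannot be reproduced from the stated inputs, because the within-woman correlation, dropout rate, sidedness and the meaning of 2.5% (relative or absolute) are not given. One set of assumptions comes close: relative 2.5% (0.025 × 16.5 = 0.4125 points), two-sided, correlation 0.5, so the SD of change is 2.1. Then n = (2.1 × (1.960 + 0.842) / 0.4125)², rounded up to 204, and 204 / (1 - 0.18) = 249. The point below does not depend on this.

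**Rule as printed (exclude strain ≤ -16%).**
- a = (-16 + 16.5) / 2.1 = 0.238
- Excluded: Φ(0.238) = 0.594, or 59.4%. The plan's mean woman, at -16.5%, is among them.
- Kept: 40.6%, with mean -16.5 + 2.1 × φ(a) / (1 - Φ(a)) = -16.5 + 2.1 × 0.388 / 0.406 = -14.5% and SD 1.18.

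**Direction reversed (exclude strain weaker than -16%).**
- Excluded: 40.6%.
- Kept: 59.4%, with mean -16.5 - 2.1 × 0.388 / 0.594 = -17.9% and SD 1.36.

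**Assessments needed to enrol 250, on this criterion alone.** As printed, 250 / 0.406 ≈ 616; reversed, 250 / 0.594 ≈ 421.

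**Sensitivity of the printed rule.**

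| Mean | SD | Excluded as printed |
|---|---|---|
| -16.5 | 1.5 | 63.1% |
| -16.5 | 2.1 | 59.4% |
| -16.5 | 2.5 | 57.9% |
| -16.5 | 3.0 | 56.6% |
| -18 (assumed) | 2.1 | 83% |
| -20 (assumed) | 2.1 | 97% |

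The last two means are illustrations only and do not come from the documents.

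**Regression to the mean with no radiation effect.** Expected drift is (1 - ρ) × (distance of the kept mean from -16.5), with the population mean and SD unchanged at follow-up. The correlation ρ is assumed, because the documents give none.

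| ρ | As printed (distance 2.01): drift towards stronger | Reversed (distance 1.37): drift towards weaker |
|---|---|---|
| 0.5 | 1.00 points | 0.69 points |
| 0.7 | 0.60 points | 0.41 points |
| 0.9 | 0.20 points | 0.14 points |

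If the 2.5% endpoint is relative, it equals about 0.41 points. The printed rule would tend to hide harm and the reversed rule to imitate it. Centres that read the sign differently would carry opposite biases.

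**The case against.** The strongest reply is that this is a slip of notation that clinicians would read through. The criterion is labelled abnormal, it stands beside low LVEF and abnormal wall motion, and the plan elsewhere speaks of strain in terms of magnitude: a decrease means loss of function, although the signed value rises. Read that way, the threshold means weak strain. A literal reading would remove most women and would probably be noticed. Nothing in the documents shows how sites applied it.

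That has force on the consequence: harm to enrolment is conditional on literal use. It does not rescue the text. The minus sign is printed on both thresholds in both places, no absolute-value convention is stated, and the form tells the site to exclude.

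Two further objections stand as refinements. First, the mismatch with section 9.2 is not caused by the sign alone. Either direction leaves a cohort unlike the planning population (-14.5% or -17.9%, against -16.5%), because the cut-off lies so close to the planned mean. Second, turning the inequality round leaves regression to the mean to be dealt with, now in the direction that resembles radiation damage.

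**Conclusion.** The point holds. On the plan's own signed scale, section 4 and the ECHO-ST form exclude the stronger hearts and admit the weaker ones, for strain and strain rate alike. Applied literally, the strain item alone removes about 59% of the planning population and leaves women averaging -14.5%. The direction of the error follows from the documents without any assumption. Its size rests on normality, on the cited mean and SD describing the women assessed, and on the criterion meaning global strain. Whether the cohort was affected depends on how sites applied the rule, which the documents do not show. Because this is an eligibility threshold that sites and monitors must apply as written, it must be corrected.

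**What to change.** 1. In section 4 and the ECHO-ST form, turn both strain inequalities round so that abnormal means weaker deformation. Preferably state them on absolute values, say whether global strain is meant, and give strain rate per second. The cardiology lead should confirm the cut-off values; none is proposed here.
2. Reconcile the confirmed rule with section 9.2. Reversing the direction at the printed cut-off would still exclude about 41% of the planning population, so the baseline mean and SD behind the sample size need restating for the women actually eligible.
3. Use the same absolute-value convention for a decrease in section 3.2.1.
4. Add the echocardiographic exclusion to the CRF ELIGIBILITY form. Section 4 refers readers there for details, but the form omits it.
5. In section 9.3, say how the before-after comparison allows for selection on baseline strain. One option is to rest inference on the dose-response comparison within the cohort, where drift common to all women largely cancels, provided that every centre applied the same rule.
6. Check how each centre has applied the rule. Section 7.2 counts women as included at consent, before the echocardiogram is required, so the check must cover women included and later removed as well as those still in the study.

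The text changes are a few lines in the protocol and two forms. The real cost is the look-back and restating the sample-size assumptions.

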## **5. TRIAL DESIGN**

MEDIRAD EARLY HEART is a multicentre prospective cohort study that will include 250 female BC patients treated with post-operative RT alone after primary breast conserving surgery to assess imaging and circulating cardiac biomarkers the first 2 years following RT.

## **6. THERAPEUTIC REGIMENS, EXPECTED TOXICITY, DOSE MODIFICATION**

### **6.1. Radiotherapy**

All patients will undergo computerized tomography (CT) in treatment position to prepare the treatment plan.

### **6.2. Patient positioning**

The patient will be immobilized with an appropriate immobilization aid in supine position. Patients will be treated according to own center specificities (active breathing control for left BC, for left and right BC, ...) in order to lower the cardiac dose as much as possible.

### **6.3. Planning CT scan acquisition**

A planning CT-scan is made with the patient in treatment position with the immobilisation device in place, according to own center specificities regarding breathing control. Slice thickness of maximum 2 mm will be used

Images will be constructed with at least 512 x 512 pixel matrix. DRRs (digitally reconstructed radiographs) of all beams including the orthogonal verification beam pair will be generated from the planning CT scan for comparison with portal images.

#### **6.4. Target volumes and organs at risk**

The definition of target volumes will be in accordance with the ICRU 50 report.

##### **6.4.1. Gross tumour volume (GTV)**

Not applicable.

##### **6.4.2. Clinical target volume (CTV)**

The CTV includes the entire breast with the exclusion of the skin (5 mm).

##### **6.4.3. Planning target volume (PTV)**

To account for set up errors, a CTV-PTV margin is used according to institutional standards.

##### **6.4.4. Organs at risk (OAR)**

For all centres of investigation, the following OAR will be delineated: Contralateral breast, lung, heart.

In addition, other OAR could be delineated according to the routine of centres: heart structures, LAD coronary, oesophagus and thyroid (in case of periclavicular lymph nodes are irradiated).

#### **6.5. Treatment planning**

The total dose for the breast will be in accordance with center practices (50 Gy/25 fractions, or 40.05 Gy/15 fractions or isoeffective schemes). The possible boost can be applied with photons or electrons both sequentially or simultaneously.

##### **6.5.1. Limit of dose in organs at risk**

In all cases, dose will be prescribed according to the ICRU criteria and dose constraints are according to QUANTEC. Algorithms are used for the calculation of the dose distribution, considering lack of homogeneity in the tissue

##### **6.5.2. Irradiation techniques**

The treatment techniques based on planning-CT scan consist of 3D-CRT, IMRT, or VMAT/RapidArc.

##### **6.5.3. Patient position verification**

To ensure quality of positioning, patient positioning is verified. This can be done with MV imaging (Electronic Portal Imaging Device, EPID) or with kV imaging (cone beam CT).

## 7. CLINICAL EVALUATION, LABORATORY TESTS AND FOLLOW-UP

### 7.1. Before inclusion

In each centre, radiation oncologists will enable first contact with women diagnosed with breast cancer: during first visit with the radiation oncologist, he/she will present the study and its implications to women patients for whom radiation therapy is planned. This consultation is 1 to 4 weeks before the start of radiotherapy, depending on the center. The radiation oncologist will ensure that women meet the criteria for inclusion in the study and study information leaflet detailing the protocol will be given with a consent form (► see *INFORMATION LETTER* and *INFORMED CONSENT FORM* in Appendix).

### 7.2. Before start of treatment protocol

About 1 to 2 weeks before the start of radiotherapy, during the visit for the RT planning-CT, women agreeing to participate in the study will give their signed written informed consent form and will then be considered as included. Cardiac MRI will not be mandatory for inclusion in EARLY HEART Study (in contrast with ECHO-ST, CT and BLOOD).

► See *CRF ELIGIBILITY*, *CRF CANCER*, *CRF planned RT* and *CRF CARDIOLOGY*, in appendix for further details

From this inclusion visit on, women's follow-up protocol will be realized. Before start of RT the following interventions will have to be performed:

- Cardiac imaging:
  - An electrocardiogram to detect any arrhythmia followed by an Automated 2D-speckle-tracking echocardiography (ECHO-ST) the most commonly used modality to evaluate myocardial dysfunction and a new technique of assessing myocardial deformation;  
► See *CRF ECHO-ST* in appendix for further details
  - Computed tomography (CT) by using both low dose non enhanced and enhanced CT scans to evaluate coronary artery lesions by assessing morphological information including plaques and stenosis of the arteries, and determination of the CAC score;  
► See *CTCA PROTOCOL* and *CRF* in appendix for further details
  - Cardiac magnetic resonance imaging (MRI) for the measurement of ventricular function, size of the two heart chambers, and wall thickness; tissue characterization by delayed enhancement; and pre-/post-contrast T1 mapping mapping and pre contrast T2 mapping of the left ventricle.  
► See *MRI PROTOCOL* and *CRF* in appendix for further details
- Circulating biomarkers (BLOOD) will be based on a panel of circulating classical and novel blood-based biomarkers (see 7.5 *Blood samples for biomarkers analysis* for further details)

Furthermore, toxicity will be assessed according CTCAE 4.03 and patient rated outcome

measures. ► See *CRF TOXICITY in appendix for further details*

### **7.3. During treatment**

As planned in routine follow up of patients in each center, toxicity will be assessed according CTCAE 4.03 and patient rated outcome measures.

### **7.4. Subsequent follow-up**

During subsequent follow up imaging and circulating biomarkers will be assessed at specific time points after RT up to 24 months:

- At the end of RT: BLOOD.
- Six months after RT: ECHO-ST, MRI, BLOOD.
- Two years after RT: Electrocardiogram and ECHO-ST, MRI, CT, BLOOD.

Furthermore, in addition to routine follow-up of patients in each center, acute and late toxicity will be assessed according CTCAE 4.03 and patient rated outcome measures at the end of RT, 6 months, and 24 months after RT.

### **7.5. Blood samples for biomarkers analysis**

Each patient will have 4 blood samples. For each blood sample, 30mL of blood will be collected and divided in 6 tubes of 5 mL as follows: 2 tubes heparin; 2 tubes EDTA; 2 tubes CITRATE (2 x 5ml).

Blood samples will be collected: before RT, at the end of RT, 6 months after RT and 24 months after RT. Once blood sample is collected, a standard operation procedure will be followed ► See *BLOOD PROTOCOL in appendix for further details*.

All prepared aliquots of 500 µl (approximately 30 aliquots per patient per blood sample) will be stored and freeze at –80°C in the local investigating center for a short time period of few weeks or months (depending on the capacity of storage of the local center), and then periodically sent with a medical specialized carriers to University of Bristol which is the centre for central storage of aliquots for biomarkers analysis (Workpackage 4.2.2 Preclinical and clinical identification of standard and innovative biomarkers of radiation-induced cardiovascular toxicity).

All blood samples and aliquots will be labelled using the same anonymised code assignment for patient as the one used in CRF.

Once received at University of Bristol, for each patient at each time of blood sample, 20 aliquots will be used for biomarkers analysis, the 10 remaining aliquots will enter a long term storage collection for 15 years. After 15 years, all aliquots will be destroyed except if a patient asks for early destroy of her aliquots. Aliquots of the long term storage collection could only be used in the frame of research on cardiovascular diseases.

Responsible party for EARLY HEART aliquots collection: Pr [name], Bristol Heart

Institute, School of Clinical Sciences, University of Bristol, Bristol Royal Infirmary, [name], [name], Bristol, United Kingdom.

## 8. FLOWCHART

The flow chart below gives an overview of the EARLY HEART study design and the main procedures that subjects will undergo during this research.

In the Standard Follow-up Program only toxicity assessment (CTCAE 4.03) is performed. ECHO-ST, CT, MRI and BLOOD are performed for the research study.

	Baseline	At the end of RT	6 ms	24 ms
Informed Consent	X			
In- and exclusion criteria	X			
Medical history	X			
Electrocardiogram (ECG) followed by ECHO-ST	X		X (ECHO alone, no ECG)	X
CT	X			X
MRI	X		X	X
BLOOD	X	X	X	X
Toxicity assessment (CTCAE 4.03)		X	X	X

## 9. STATISTICAL CONSIDERATIONS

### 9.1. Study Design

**MEDIRAD EARLY HEART** is a multicentre prospective cohort study that will include female BC patients treated with post-operative RT alone after primary breast conserving surgery to assess imaging and circulating cardiac biomarkers the first 2 years following RT.

### 9.2. Sample Size

The sample size was based on a statistical power of 80%, an alpha-risk of 5%, the definition of the primary endpoint (a decrease in the global and segmental longitudinal strain or strain rate of at least 2.5%) and baseline measurements hypothesis (mean global longitudinal strain before RT : -16.5%  $\pm$  2.1% from Dalen et al, European Journal of Echocardiography : the Journal of the Working Group on Echocardiography of the European Society of Cardiology. 2010) Considering paired test for comparisons, but also possible lost to follow-up due to death or other reason, the inclusion of 250 women is necessary for EARLY-HEART study.

Centre	Recruitment rate per month	Total number of patients to recruit in 1 year
IRSN	4.2	50
UMCG	5	70
TUM-MED	4.6	55
CCUL	2.1	25
ICO	4.2	50
Total		250

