### 1.7. Statistical considerations:

With 250 women, the study will have 80% power, with an  $\alpha=0.05$  to find a mean decrease in GLS/GLSR of at least 2.5%.

The analysis plan is divided into three parts. In the first part a descriptive analysis of the data is done. Differences in biomarkers between unexposed and paired exposed groups (e.g. right vs. left-sided breast RT) at different time points are analysed to generate preliminary hypotheses on effects of RT on the heart. To investigate the time course of continuous variables extracted from ECHO-ST, CT or MRI measurements, mixed regression models are used. In the second part (anatomical) changes in cardiac biomarkers are correlated with dose distribution data. In the third part of the analysis multivariable Normal Tissue Complication Probability (NTCP) models are constructed. An integrative clinical-biological risk score is developed for individual risk prediction.

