## 3.2. Endpoints

### 3.2.1. Primary endpoints

The primary endpoints are defined as a mean decrease in Global Longitudinal Strain or Global Longitudinal Strain Rate, determined by cardiac ECHO-ST, of at least 2.5% between baseline and 24 months after RT (*Erven et al, Int J Radiation Oncol Biol Phys, 2012; Lo et al, In J Radiation Oncol Biol Phys, 2015*).

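### The before-after change in global longitudinal strain has no comparator and starts from the same echo that screens women on strain, so regression to the mean can move it without any radiation effect; 9.2 and 9.3 should say so and say where attribution rests

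*Combined protocol and SAP*

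**What the plan says.** - **Endpoint.** Section 3.2.1 defines the primary endpoint as a mean decrease in GLS, or in its rate, "of at least 2.5% between baseline and 24 months after RT". No comparison group enters this definition.
- **Sample size.** Section 9.2 assumes a baseline mean of -16.5% with SD 2.1%, 80% power and 5% alpha, and concludes: "Considering paired test for comparisons, but also possible lost to follow-up due to death or other reason, the inclusion of 250 women is necessary". Section 1.7 repeats it: "With 250 women, the study will have 80% power".
- **Screen.** The exclusion criteria in section 4 remove women with an abnormal pre-radiotherapy echo, "Abnormal echocardiography before radiotherapy defined as: LVEF<50%; longitudinal strain" at or below -16% being one of the conditions. The local ECHO-ST form in the appendix repeats the rule. The flowchart in section 8 shows one baseline echo, so the same reading screens the woman and starts her change score.
- **Analysis.** In 9.3 the paired tests sit in Stage I, which is headed as descriptive. Stage II models the relation between cardiac dose and change over time, in line with the specific objective in 3.1. It lists several ways to enter dose and selects none.
- **Internal contrast.** Section 1.7 also plans "Differences in biomarkers between unexposed and paired exposed groups (e.g. right vs. left-sided breast RT", to generate preliminary hypotheses. Section 9.3 does not carry this contrast forward.

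**The concern.** A woman kept because one reading passed the cut will, on average, read closer to the population mean at her next echo, whatever radiotherapy does. With no comparator, the primary change cannot separate this shift from a radiation effect. The primary objective concerns radiation-induced changes, and the stated power belongs to the paired change. A significant fall in GLS, the result the study is powered to find, could therefore be reported as radiation damage when part or all of it comes from selection. If the cut works in the printed direction, the shift goes the other way and could conceal real damage. Neither 9.2 nor 9.3 mentions selection on baseline or says which analysis supports attribution.

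**Working it through.** **Inputs from the documents.** Mean 16.5 and SD 2.1 in magnitude (9.2); cut 16 (section 4 and the ECHO-ST form); effect 2.5%; 80% power; 5% alpha.

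**Assumptions.** Two-sided test; 2.5% read as relative, so 0.025 x 16.5 = 0.4125 points; normal distribution; baseline to 24-month correlation r = 0.5 / 0.7 / 0.8 / 0.9. The documents do not give r, the true mean or a dropout rate.

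**The plan's 250.** With SD of change 2.1 x sqrt(2(1 - r)), which is 2.1 at r = 0.5, the paired need is 204 by normal approximation and 206 by noncentral t. Then 250 allows for a loss of 1 - 204/250 = 18.4%. So 250 is compatible with the inputs but cannot be derived from them. At r = 0.7 / 0.8 / 0.9 the need falls to 124 / 84 / 43. I keep 206 pairs below.

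**Selection at the planning mean, cut read by magnitude.**
- Distance of cut from mean: (16.5 - 16)/2.1 = 0.24 SD.
- Excluded 40.6%, kept 59.4%. Kept mean 17.87, a shift of 1.37. SD of kept readings 1.36.
- Null fall = (1 - r) x 1.37 = 0.69 / 0.41 / 0.27 / 0.14 points. At r = 0.7 this equals the whole 0.41-point target.
- SD of change = sqrt((1 - r)^2 x 1.36^2 + 2.1^2 x (1 - r^2)) = 1.94 / 1.55 / 1.29 / 0.93.

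**Null trials giving a significant paired decrease (noncentral t), and null trials whose observed fall reaches 2.5% of the kept mean (normal approximation).**

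| True mean | Removed by cut | Significant decrease, r = 0.5 / 0.7 / 0.8 / 0.9 | Reaches 2.5% |
|---|---|---|---|
| 16.5 | 41% | 99.9 / 97 / 86 / 56% | 96 / 37 / 3 / 0% |
| 18 | 17% | 63 / 41 / 29 / 16.5% | 15 / 1 / 0 / 0% |
| 20 | 3% | 7 / 6 / 5 / 4% | essentially never |

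The nominal rate of false decreases is 2.5%. If 2.5% means absolute points, the threshold is not reached, because the largest null fall is 0.69 points.

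**If 250 is counted before the echo exclusions.** 250 x 0.594 leaves about 148 women, and 148 x 0.816 about 121 pairs. False decreases at mean 16.5 are then 97 / 82 / 64 / 37%.

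**Cut read as printed.** Values at or below -16% are excluded, so weaker strain is kept. The kept mean is 14.49, a shift of 2.01, and the null change is an apparent improvement of 1.00 / 0.60 / 0.40 / 0.20 points.

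**Estimating the shift from planned echoes.** Regression to the mean = [variance of (24-month minus 6-month GLS) in kept women / 2] / variance of pre-radiotherapy GLS in all women echoed x (kept mean - mean of all echoed). At r = 0.7: (2 x 2.1^2 x 0.3 / 2) / 2.1^2 x 1.37 = 0.41, equal to the null fall above. This assumes independent, equal echo error at the three visits.

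**The case against.** The strongest reply is that the plan already contains the remedy. Stage I is labelled descriptive, Stage II models dose against change, the specific objective is that dose relation, and the outline names a right-left contrast. All women pass the same screen, so regression to the mean should largely cancel in comparisons between them. This stands, and it rules out a reading some may be tempted to make: that the whole study lacks a comparator or cannot attribute anything to radiation. What remains is that no passage ties the primary change to these analyses, and that the stated power is for the change alone.

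A second reply is that the high false-positive rates belong to a mean of 16.5, which sits badly with a cut that would then remove 41% of women. That also stands. A reader might infer that a false finding is nearly certain, but the documents do not support this. The range runs from negligible to large, and the threshold in 3.2.1 is met far less often than simple significance.

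Third, the printed sign might suggest that sites exclude women with stronger strain. The text shows only that the printed inequality conflicts with the word for abnormal. It is not evidence of practice.

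**Conclusion.** The concern holds as a gap in 9.2 and 9.3. The pooled change in GLS can be biased by selection on its own baseline, and the plan neither says so nor states where attribution rests. The mechanism follows directly from the documents; its size does not. Under the stated assumptions the null fall at mean 16.5 is 0.14 to 0.69 points against a relative target of 0.41. It is smaller at mean 18 and negligible at mean 20. The direction depends on how the cut is read: by magnitude it imitates damage, as printed it can mask it. The study is not invalidated, and this point does not dispute the number 250.

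**What to change.** In 9.2 and 9.3:

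1. State that the pooled before-after GLS change is not by itself evidence of a radiation effect, and that attribution rests on the Stage II dose-response model. Name one lead dose metric in advance and include centre or echo system as a term; the ECHO-ST form already records "Name and version of the of the ultrasound system". Carry the right-left comparison into 9.3 as supporting evidence between groups, not paired, since the two sides are different women.
2. Report the mean, SD and share excluded for pre-radiotherapy GLS in all women echoed, and show the estimated regression to the mean beside the pooled change. The form records the value and section 7.2 places consent at inclusion, but use of excluded women's data depends on consent wording not available here.
3. State that the 80% power applies only to the paired change.
4. Reconcile the printed sign of the strain exclusion in section 4 and the ECHO-ST form with the word abnormal. Reconcile the cut with the -16.5% planning mean. Say whether 250 is counted before or after the echo exclusions.

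**Cost.** No new examination, but probably a substantial amendment under 12.8. Power for attribution is lower. For a left-right difference of 0.4125 points with an assumed 103 women per side, it is about 33 / 47 / 63 / 89% on the change (SD 1.94 / 1.55 / 1.29 / 0.93) and 37 / 50 / 65 / 90% adjusted for baseline (SD 2.1 x sqrt(1 - r^2)), at r = 0.5 / 0.7 / 0.8 / 0.9. The regression estimate does not remove ageing, endocrine therapy or echo drift, and falls that differ between women from 6 to 24 months would distort it.
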